4.1 Study Participant Disposition

All patients who discontinue from the study will be identified, and the extent of their participation in the study will be reported by the sponsor in the Clinical Study Report. If known, a reason for their discontinuation will be given.

4.2 Study Participant Characteristics

The following variables will be recorded and may be used as quantitative or classification variables:

- Patient characteristics, measured at V1:
 - Study center
 - Patient's sociodemographic characteristics: age, sex and other demographic characteristics
 - Recent analgesic treatment history
 - Personality questionnaires, at facet- and domain-level: Multidimensional Health Locus of Control Scale (MHLCS, with domains I, C and P), Hospital Anxiety and Depression Scale (HADS), Revised Life Orientation Test (LOT-R) and Expectation.
 - Pain evaluation questionnaires: Douleur Neuropathique en 4 questions (DN4), Neuropathic Pain Symptom Inventory (NPSI), and Pain Catastrophizing Scale (PCS)
- Pain and quality of life assessment, measured at V1 and V2:
 - Brief Pain Inventory (BPI)
 - Quality of Life questionnaire in 30 questions (QLQ-C30), IGAC, PGAC
 - Clinical Pain Assessment (CPA): Static Allodynia (SA), Dynamic Mechanical Allodynia (DMA), Mechanical Pain Threshold (MPT), Thermal Pain Sensitivity (TPS)
- Follow-up from the daily diary and intermediate visit:
 - Daily Average and Worst Pain Score (APS and WPS),
 - Daily analgesic therapy (including rescue medication): number of distinct drugs intaken, number of distinct drug categories intaken
 - Intake of rescue analgesic treatment if any,

Note that the description of analgesic therapy hereabove requires the grouping of drugs into a small number of classes which will be described in the Statistical Analysis Report.

The collection of the values of all these variables and variables derived from them for a single patient is referred to as *the patient-vector* below in the text.

5 Description of the Analyses

The final statistical analysis covers four aspects (Ax) detailed in the following sections:

- A1: Descriptive statistics at baseline, covering secondary objectives number 1 and 2.
- A2: Evolution of daily pain and treatments, covering secondary objective number 3.
- A3: Prediction of treatment efficacy, covering the primary objective

In addition, the interim statistical analysis will cover the following two aspects, corresponding to the interim objectives:

- I1: Sample size computation for the prediction of treatment efficacy.
- I2: Relation between psychological traits and pain evolution

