In approximately two thirds of cancer pain, pain is directly related to the presence of primary or metastatic disease and one third is linked to the treatment itself i.e. radiation, chemotherapy induced peripheral neurotoxicity (Cavaletti et al., 2010), post-mastectomy (Nogueira-Fabro et al. 2012), or postoperative pain after lymph node biopsy (Høimyr et al. 2011), immobility.

Different components of CIBP

At least theoretically, to maximize the likelihood to select the right therapy for a patient suffering from CIBP, a correct assessment of the CIBP level and evolution should be performed. This assessment should take into account the specific features of CIBP at the level of the patient. These are briefly summarized below.

The main physiological components of CIBP are the neuropathic components associated with the inflammatory process of pain but linked to specificities of bone. In addition, the other physiological component is connected to disruption of bone homeostasis (nociceptive component). Drivers of nociceptor activation are the local release of algogenic substances related to bone osteolysis and inflammation, and the occurrence of micro fractures, increased pressure within bone, periosteal stretching, and damage to adjacent tissues (Mercadante 1997). Because these processes activate intact nociceptors, bone pain now may be viewed as a mixed nociceptive and neuropathic pain, which presumably is determined by a variable and dynamic set of events that activate some normally-functioning nerves while simultaneously causing aberrant somatosensory processing by others (Jimenez-Andrade et al. 2011, Middlemiss et al. 2011).

Short overview of CIBP treatments today – Application of WHO

Today many therapies are available to lessen CIBP although they remain largely unsatisfactory. These treatments include drug therapies, medical treatment and procedures (such as External beam Radiation Therapy (XRT), surgery (radiofrequency ablation, vertebroplasty...), non-drug therapies and supportive care. The treatments used mainly depend on the location and the severity of CIBP. Although palliative XRT (radiotherapy) remains the gold standard to treat CIBP, not all patients respond evenly to the treatment and not all of them can benefit from the needed infrastructure. Accordingly, drug therapies remain the most widely used either alone or in combination with additional non-drug therapies.

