2.1 Primary Objective (for the whole study)

To define predictive factors of pain management/treatments efficacy in cancer patients with bone metastases suffering from pain (or cancer-induced bone pain (CIBP)), based on individual patient disease, therapy history, personality traits and expectation.

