2.2 Secondary Objectives

- 1. To identify groups of patients showing similar profile at baseline, in terms of personality traits and disease history
- 2. To measure the concordance between questionnaire-based and clinical pain assessment
- 3. To identify typical evolution of pain level among cancer patients with bone metastases

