2.5 Secondary Endpoints

- Individual analgesic treatment efficacy: Patient's daily APS and the linear regression coefficient of its daily evolution
- Individual analgesic treatment efficacy: Patient's change from baseline of
 - Pain severity, as measured by the weekly means of the daily Worst Pain Score (WPS),
 - Pain severity and interference as measured by the Brief Pain Inventory (BPI),
 - Investigator and Patient Global Assessment of Changes (IGAC and PGAC),
 - Pain intensity measured after Clinical Pain Assessments (CPAs) at Visit 2,
 - Quality-of-Life Questionnaire in 30 questions (QLQ-C30).
- Correlation between pain severity and clinical pain assessment as measured by:
 - Pain severity, as measured by the weekly Average Pain Score (APS) at Visit 1 and 2,
 - Pain intensity measured after Clinical Pain Assessments (CPAs) at Visit 1 and 2.

Variables used as predictive factors rather than as endpoints are described hereunder in Section 4.2.

3 Summary of Study Design

See the latest protocol version.

4 Populations for Analyses

Statistical analysis and data tabulation will be performed using the population of completers unless specified otherwise. This set includes all data from patients who have been screened, included and who completed the study (no drop-outs).

For the interim analysis, only patients who completed the study before the interim database transfer will be included.

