5.1 A1: Descriptive statistics at baseline

This section provides general information useful before starting any data analysis. Only variables at baseline are analysed at this point, so that any decisions taken are not influenced by the observed response to treatment. The variables covered are: sociodemographic characteristics, recent analgesic treatment history, personality questionnaires, pain (including CPA) and quality of life at visit 1.

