5.3 A3: Prediction of treatment efficacy

A predictive model will be tuned based on the characteristics at V1 in order to predict the efficacy of each treatment on the patient. One model will be built for each treatment t, with the following design:

- Scope: patients having received treatment t on some but not all days
- Response (target): Per-patient treatment effect, as measured by the average difference of daily APS between the days with and without treatment t
- Predictors: patient characteristics at baseline

The performances of these pre-treatment models will be evaluated inside a resampling procedure. This procedure repeatedly samples 80% data to learn a predictive model whose predictive performances are assessed on the 20% remaining unseen data. In total, 200 train-test splits are performed for each treatment. The predictive model in use will be a ridge regression, as implemented by glmnet::cv.glmnet in R, with parameter alpha=0.

Table (tab-pred-perf) will report the average predictive performance on the test sets for each treatment, in terms of relevant statistics.

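### The SAP's predictor lists leave out primary disease history and primary disease treatment history, which the objectives call for and the protocol collects

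*SAP*

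**What the plan says.** **Objectives.** SAP Section 2.1, like Protocol Section 2.1, seeks predictive factors of treatment efficacy "based on individual patient disease, therapy history, personality traits and expectation". Secondary objective 1 in SAP Section 2.2 is "To identify groups of patients showing similar profile at baseline, in terms of personality traits and disease history".

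**Predictor list.** SAP Section 2.5 states: "Variables used as predictive factors rather than as endpoints are described hereunder in Section 4.2". Among the Visit 1 patient characteristics in Section 4.2 are study centre, sociodemographic items, "Recent analgesic treatment history", the personality and expectation questionnaires, and DN4, NPSI and PCS. The section then adds pain and quality-of-life measures at Visits 1 and 2, and diary variables. The patient-vector is defined as "The collection of the values of all these variables and variables derived from them for a single patient".

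**Analyses.** Section 5.1 (A1, assigned to secondary objectives 1 and 2) says: "The variables covered are: sociodemographic characteristics, recent analgesic treatment history, personality questionnaires, pain (including CPA) and quality of life at visit 1". A2.3 and I2 correlate each Visit 1 patient characteristic with the APS trend. A3, which carries the primary objective, specifies "Predictors: patient characteristics at baseline".

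**Data collected.** Protocol Section 4.1.1 has the site record, at the enrolment visit, the history of the primary disease and of its treatment, as well as analgesic history for the preceding month. Attachment 2 gives these separate rows at Visit 1A. Protocol Section 10.1.1.1 names CRF entries among the possible sources for the patient data vectors.

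**The concern.** The objectives promise an answer about disease and therapy history, the sites collect the data for it, and the analysis plan then has no place for most of it. This does not look like a considered narrowing. SAP Section 1.2 lists the changes from the protocol, and the loss of these variables is not among them.

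The protocol treats this domain as central. Section 3.2 faults current practice for neglecting patients' own disease and therapy history, Section 3.3 names primary disease history in the study's aim, and Section 4.2.1 justifies the larger sample partly by the inclusion of patient history among the features.

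Three things are at stake: the disease-history part of secondary objective 1; the ability of the primary analysis to find or rule out a disease or cancer-treatment predictor; and the second interim objective, which includes confirming the historical data to be collected. I2 can inform that objective only for variables in its list.

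**Working it through.** The plan has no figure to reproduce on this point. The check sets what is asked for against what is collected and what is analysed.

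| Domain | Asked for in | Collected at enrolment | SAP 4.2 | SAP 5.1 |
|---|---|---|---|---|
| Personality traits | Primary objective; secondary objective 1 | Yes (Visit 1, or Visit 1B in the two-visit scenario) | Yes | Yes |
| Expectation | Primary objective | Yes | Yes | Yes, if read as one of the personality questionnaires, as 4.2 does |
| Therapy history: analgesics | Primary objective | Yes, past month | Yes | Yes |
| Therapy history: primary disease treatment | Primary objective, read with the protocol's separate collection | Yes | No | No |
| Disease: current pain state | Primary objective, on a narrow reading | Yes (DN4, NPSI, BPI, CPAs) | Yes | Partly: pain, CPAs and quality of life; DN4 and NPSI not named |
| Disease: primary disease history | Secondary objective 1; primary objective on the ordinary reading | Yes | No | No |

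1. *Is Section 4.2 the operative list?* Section 2.5 sends the reader there for the predictive factors, and the patient-vector is confined to the listed variables and those derived from them. Primary cancer type or prior cancer treatment cannot be derived from any listed variable.
2. *Does A1 widen it?* No. The Section 5.1 list is closed and its only history item is again analgesic. The A1.3 clustering therefore runs without a disease-history variable.
3. *Do A2.3, I2 or A3 widen it?* No. Each draws on the Visit 1 or baseline patient characteristics.
4. *Count.* Secondary objective 1 names two domains, and one has variables. The primary objective names four: two are covered in full (traits, expectation), therapy history is covered for analgesics only, and disease is covered only through the current pain state.
5. *What adding variables costs in multiplicity.* A2.3 and I2 use Benjamini-Hochberg (BH) correction. Assume a level of 0.05, so that with m features the strictest threshold, for the smallest p-value, is 0.05/m. The SAP does not give m. For an assumed m of 20, 30 or 50, adding three single-column features changes it as follows:
   - m = 20: 0.05/20 = 0.00250 to 0.05/23 = 0.00217, a fall of 3/23 = 13%
   - m = 30: 0.05/30 = 0.00167 to 0.05/33 = 0.00152, a fall of 3/33 = 9%
   - m = 50: 0.05/50 = 0.00100 to 0.05/53 = 0.00094, a fall of 3/53 = 6%

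   More indicator columns would cost proportionately more.

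**The case against.** **The list is permissive.** Section 4.2 says its variables may be used, the SAP allows further exploratory analyses, and the protocol admits CRF entries as inputs. So a disease variable could still be examined later. That stands, but it would be a post hoc addition: permission to leave out a listed item does not pre-specify an unlisted one.

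**The objectives can be read narrowly.** Therapy history could mean analgesic history, and patient disease could mean the pain condition. This partly answers the point for the primary objective. It does not supply disease history for secondary objective 1.

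**The table templates may list more.** The SAP refers to an attached spreadsheet that was not available for this review. It could name extra variables, but Sections 4.2 and 5.1 would still disagree with it.

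**Stronger readings that the documents do not support:**
- *That secondary objective 1 cannot be met at all.* Clustering on personality traits goes ahead as written; only the disease-history part lacks a variable.
- *That omitted radiotherapy biases the trait or drug findings.* The protocol does say "Although palliative XRT (radiotherapy) remains the gold standard to treat CIBP", and it admits patients with or without a radiotherapy programme. But the same section says that response and access vary and that drugs are the most widely used option. In A2.3, bias in a trait's correlation would also need radiotherapy to be associated with that trait, and nothing in the documents shows this. Without it, radiotherapy adds noise.
- *That A2.3 should adjust for radiotherapy during follow-up.* A2.3 is a set of marginal correlations with no covariates, adjusting for a post-baseline treatment is contestable when seeking baseline predictors, and the follow-up schedule row names only cancer concomitant medications.
- *That the loss can be stated as power.* A single-test calculation at 140 patients would ignore the BH correction and need an assumed effect size. A3 is a ridge model without a hypothesis test, run for each treatment only in patients who took it on some but not all days, a number the documents do not give.

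**Conclusion.** The point holds as a mismatch between the objectives and the analysis variables. Primary disease history and primary disease treatment history are called for and collected, but are absent from the operative predictor list and the closed A1 list, with no declared exclusion. The effect is that one of the two domains of secondary objective 1 is empty, and four analyses (A1.3, A2.3, I2 and A3) cannot take this history into account. No numerical size can be given.

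The conclusion rests on two readings. The first is that Sections 2.5 and 4.2 together fix the predictor set. The second, needed only for the cancer-treatment part, is that therapy history includes treatment of the primary disease. No objective names radiotherapy, and no collection item visible in the documents does so; whether it was captured under primary disease treatment history has to be checked on the CRF.

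**What to change.** Add a small number of coded baseline features to SAP Sections 4.2 and 5.1: primary cancer type, primary disease history, and primary disease treatment history, including radiotherapy before or at enrolment where the CRF records it. Name them as inputs to the A1.3 clustering, to A2.3 and I2, and to the A3 models. Fix the coding before outcome data are examined, and say how a categorical item such as cancer type enters A2.3 and I2, which specify only correlations.

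If the omission is intended, list it with a reason in SAP Section 1.2 and narrow the primary objective and secondary objective 1 to match.

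The first route costs an SAP edit and the coding of data the protocol already collects. It also puts a few more features under BH correction and into the per-treatment ridge models, whose sample sizes are unknown; this is a reason to keep the added set short. The second route costs only text, but gives up part of the stated question.

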5.1 A1: Descriptive statistics at baseline

This section provides general information useful before starting any data analysis. Only variables at baseline are analysed at this point, so that any decisions taken are not influenced by the observed response to treatment. The variables covered are: sociodemographic characteristics, recent analgesic treatment history, personality questionnaires, pain (including CPA) and quality of life at visit 1.

5.1.1 A1.1: Data preprocessing

Some variables may require preprocessing before being analysed. These preprocessing steps will be described here. It typically covers regrouping rare values of some categorial variables, applying logarithm transformation of some continuous variables, etc.

5.1.2 A1.2: Univariate statistics

Classical statistical information will be computed for each variable among the patient characteristics at V1. They will be listed and summarized in Table (tab-v1-summary). Descriptive statistics including subject count (N), mean, standard deviation (SD), median, first and third quartiles will be reported for continuous variables. Frequencies will be reported for categorical variables in Table (tab-v1-summary-mod). The number of missing values (NA) will also be reported for each variable. In subsequent analyses, value imputation might be performed if needed. Such cases will be documented.

5.1.3 A1.3: Outlier detection and clustering

Population outliers will be detected through a principal component analysis (PCA) visualization, reported in Figure (1). The percentage of variance captured will be documented. The patients will be colored by their study center in order to detect possible differences among the centers.

Outliers might be removed for at least parts of the further analyses. Such cases will be documented.

A clustering procedure, namely an ensemble k-Means, will be applied in order to identify subgroups of patients with intra-group similar variables at baseline, and inter-group different variables at baseline. Table (tab-v1-clustering-desc) will report per-cluster univariate statistics (median, first and third quartiles) for all variables used in the clustering procedure.

A1.4: Correlation analysis 5.1.4

The correlation between each variable (personality traits and sociodemographic variables) and the pain at baseline (APS, WPS, BPI severity, interference and QLQ-C30) will be assessed. Statistical tests for non-zero Spearman's correlation will be used. For categorial variables, exact Fisher tests will be used. Correction for multiple testing will be applied. Results will be reported in Table (tab-v1-correlations) and Figure (2). Scatterplots of the significant correlations will be produced. Figure (3) will detail the correlations within pain assessment variables and Figure (4) the correlations between personality traits and pain assessment.

5.2A2: Evolution of daily pain and treatments

Pain evolution will first be analysed on its own (secondary objective 3, i.e. without linking it to the evolution of treatments). Then, the evolution of analgesic therapies are studied, as well as their correlation with pain evolution. Due to the complexity of treatments combinations for each patient and their frequent adaptation during the follow-up period, this analysis will be made on a simple summary of the therapy evolution. Finally, the interest of each variable characterizing the patient at baseline is evaluated for its relation with the pain evolution profile.

A2.1: Summary of individual pain evolution 5.2.1

Feature extraction will be performed in order to summarize each per-patient APS evolution curve into 3 meaningful variables:

- mean APS value
- linear trend of APS
- variability of APS around trend

The linear approximation of APS was chosen in order to describe the globally increasing or decreasing trend, while keeping easily interpretable results and avoiding overfitting. How to measure these values for one patient p:

- consider a model $APS_p(t) = a_{p0} + a_{p1} t$ where p is one patient and t is the time (in days since inclusion of patient p)
- Fit weights a_{pi} by linear regression on the patient's data (one dataset per patient, one record per timepoint)
- The variability around trend is measured by the per-patient RMSE of the linear model

Univariate statistics (mean, standard deviation (SD), median, first and third quartiles) on the distribution of these variables will be reported in Table (tab-pain-evol-distr). A one-sample Wilcoxon signed rank test will be performed in order to determine whether the linear trend in APS is globally different from zero. In addition, visualisation of the patients based on these 3 features will be performed in Figure (5).

A2.2: Summary of individual analgesic treatment evolution 5.2.2

Based on the description of analysic therapy in the patient diary, the daily number of distinct drugs will be computed as well as the daily number of distinct drug categories. Treatment doses will be ignored for this analysis. The same feature extraction as in A2.1 will be performed on these daily numbers of drugs in order to obtain a per-patient average and linear trend of the number of drugs.

Univariate statistics (mean, standard deviation (SD), median, first and third quartiles) on the distribution of these variables will be reported in Table (tab-treat-evol-distr). A one-sample Wilcoxon signed rank test will be performed in order to determine whether the linear trend in number of analgesics is globally different from zero. In addition, visualisation of the patients based on these features will be performed in Figure (6).

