8.2. PHARMACODYNAMIC ASSESSMENTS

8.2.1. CLINICAL PAIN ASSESSMENTS (CPAs)

The following CPAs will be performed at enrolment, at Visit 2 and at optional intermediate evaluation Visit as specified in Sections 16.1 and 16.2 Study Schedule.

First, the painful areas (PA) will be defined by patients, using a standardized blank body map. CPAs will then be carried out by the Investigator or his/her designee on the skin overlying the most painful area (MPA) reported by the patient. The control area to compare to would be the equivalent dermatome region on the contralateral side of the body, or for central spinal sites an alternative non-painful area at the spinal level. This control area site will be defined as “normal”.

If the MPA is different at the next visit from the previous one, all assessments will be performed on the current MPA first and then again on the previous visit MPA. However, in the case scenario of the MPA at Visit 2 is different from both the one identified at intermediate evaluation Visit and the other at enrolment, only MPA defined as such at previous visit (intermediate evaluation) and at this current Visit 2 will be assessed.

Regarding MPA, clinical signs are identified as follows:

- Hypoesthesia is defined as the presence of an area where light touch of the blunt end of a paintbrush is felt less precisely than in referent control areas.
- Sensory loss is defined as the presence of an area where the same light touch as referred above is not felt at all.
- Hyperalgesia is defined as the presence of an area where the pain induced by stimulus applied perpendicularly to the skin is felt abnormally intensely.
- Allodynia is defined as the presence of an area of pain after the application of non-painful stimulus.

The centre of an area with allodynia or hyperalgesia is considered for further evaluation. However, in the absence of allodynia and hyperalgesia the centre of the area of hypoesthesia or sensory loss is then considered.

All CPAs will be carried out in a quiet environment, with a relaxed patient, previously instructed on the procedure. If a test provoked pain, the Investigator will wait for pain disappearance before proceeding with the next test. All CPAs will be completed within approximately 20 minutes.

The CPAs will include the following parameters:

The Most Painful Area (MPA)

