5.2.3 A2.3: Relation between patient's characteristics and pain evolution

For each feature from the patient characteristics at V1, the correlation will be computed with the linear trend of pain evolution defined in A2.1. A p-value for non-zero correlation will be reported too, with BH correction for multiple testing. Results will be presented in Table (tab-cor-baseline-pain-evol).

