6.2 Figures

Figure 1: Outlier detection by Principal Component Analysis based on data at baseline. The two first components are represented (Variance captured: %). Colors indicate the grouping of points into clusters.

Figure 2: Matrix of correlations between all pairs of variables at baseline (personality traits and sociodemographic variables)

Figure 3: Scatterplots of the significant correlations between the different pain measures at baseline

Figure 4: Scatterplots of the significant correlations between a personality trait and a pain measure at baseline

Figure 5: Summary visualization of the evolution of pain during follow-up period. Each point represents a patient, with average APS as abscissa and linear trend as ordinate

Figure 6: Summary visualization of the evolution of analgesic treatments during follow-up period. Each point represents a patient, with the number of different analgesic drugs (for the graph on the left) or the number of different analgesic drug classes (on the right) as abscissa, and their linear trend as ordinate

Figure 7: Learning curve for the prediction of analgesic treatment efficacy. The average performance evaluated by cross-validation on random subsets of the data is shown in ordinate, with the size of the training set as abscissa. An extrapolation curve (LOWESS) is also shown for sample sizes up to N=200.

7 Data Transfer and Unblinding Plan

The study data is collected and managed by Aepodia SA. Several information transfers will occur between Aepodia and DNAlytics, under the supervision of Tools4Patient:

Jun. 2015 **Database table structure transfer** – The objective of this transfer is to allow DNAlytics to prepare the analysis scripts and finalize the SAP. The data concerning a few included patients will be transfered in order to make the scripts creation possible. Those patients data are anonymized by Aepodia prior to the transfer to DNAlytics. Those patients will however be identified by their inclusion number.

	T2001-01 – Statistical Analysis Plan	
DNAIUtics Deterdriven personalized medicine from R&D to market access		To : T4P Auth. : [name] V1.3 - 2017-04-10

May 2017 (Est.) Interim database transfer – The objective of this transfer from Aepodia to DNAlytics is to apply the interim analysis plan described in this document. Those patients data are anonymized by Aepodia prior to the transfer to DNAlytics. Those patients will however be identified by their inclusion number.

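### The SAP's only explicit check for centre differences is a colour that the Figure 1 legend gives to clusters, and even a plot coloured by centre could miss site differences in the sensory tests

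*SAP*

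**What the plan says.** - SAP 5.1.3 (A1.3), on the PCA plot reported as Figure 1: "The patients will be colored by their study center in order to detect possible differences among the centers".
- SAP 6.2, legend of Figure 1, which shows the first two components: "Colors indicate the grouping of points into clusters".
- SAP 5.1 defines the baseline data set for A1: "The variables covered are: sociodemographic characteristics, recent analgesic treatment history, personality questionnaires, pain (including CPA) and quality of life at visit 1". The sensory tests are therefore in it.
- SAP 4.2 puts study centre first among the patient characteristics at Visit 1, all of which "may be used as quantitative or classification variables". CPAs are listed in a separate block, with the measures taken at Visits 1 and 2.
- SAP 5.2.3 (A2.3), repeated for the interim in 5.4.2 (I2): "For each feature from the patient characteristics at V1, the correlation will be computed with the linear trend of pain evolution defined in A2.1". SAP 5.3 (A3): "Predictors: patient characteristics at baseline".
- Protocol 8.2.1 has the CPAs performed by the investigator or a delegate at each site, and lets an equivalent device be substituted for SA, DMA, MPT and TPS alike.
- SAP 2.2 makes concordance between questionnaire-based and clinical pain assessment secondary objective 2. SAP 2.5 lists the correlation of APS with CPA at Visits 1 and 2 as an endpoint.

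**The concern.** One figure is given two incompatible colour codes in current text. If the programmer follows the legend, the single step whose declared purpose is to find centre differences shows none.

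Restoring the centre colours may not be enough. The CPAs depend on who performs them and with what device, so they are the baseline measures most open to site effects. They are also few beside the questionnaire scores, and a plot of the two leading components shows whatever dominates the correlation matrix. A site shift in the sensory tests that goes unnoticed would be read as a difference between patients, and would distort the APS–CPA correlation.

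**Working it through.** **1. Text against legend.** Section 5.1.3 assigns colour to centre and the Figure 1 legend assigns it to cluster. Neither passage is an amendment log, and no second centre plot is described. The two must be reconciled.

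**2. Where else centre could appear.** Read literally, centre is a Visit 1 characteristic and so falls within A2.3, I2 and A3. Those steps relate centre to the APS trend or to a per-treatment effect. None compares CPA values between sites, and the coding of a nominal, multi-level centre variable in a correlation is not given. A1.2 describes no by-centre summary.

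**3. Can two components show a CPA-only centre effect?** The plan gives no figure to reproduce. Inputs from the documents: about 140 completers (Protocol 4.2.1), 60 at the interim (SAP introduction), two components plotted. Everything else is assumed: 5 or 10 equal centres; 40 questionnaire or clinical variables plus 6 or 12 CPA variables; standardised PCA; a centre effect in the CPA variables only, at 10%, 20% or 40% of their variance, either common to all tests or separate for each; questionnaires driven by one factor or two. There were 200 runs per setting (Monte Carlo SE at most √(0.5 × 0.5 / 200) = 3.5 points).

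Detection on the plot was a one-way F test by centre on PC1 or PC2 at 0.025 each, which is more generous than judging colours by eye. The comparator was a one-way ANOVA by centre on each CPA variable, Bonferroni-corrected at 0.05. Chance detection is about 5%.

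Results at n = 140:

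| Questionnaire factors | Centre effect | CPA variables | PC1/PC2 | Direct tests |
|---|---|---|---|---|
| One | common | 6 or 12 | 84–100% | 80–100% |
| One | separate | 6 or 12 | 16–100% | 96–100% |
| Two | common | 6 | 4.5–17.5% | 77–100% |
| Two | common | 12 | 9.5–70% | 84–100% |
| Two | separate | 6 or 12 | 5–18% | 97–100% |

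At n = 60 the ranges over all settings are 5–100% on the components and 39–100% for the direct tests.

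A second simulation at n = 140 used 30 questionnaire variables, 5 or 10 CPA variables, 5 or 10 centres and a between-centre SD of 0.5. Its comparator was Kruskal-Wallis tests with BH correction.
- Two or three questionnaire factors: 5–23% on the components against 99–100% with separate shifts. With a common shift, 9–23% against 85–90% (5 CPAs) and 61–91% against 88–93% (10 CPAs).
- One questionnaire factor: 45–66% on the components (separate shifts) and 94–100% (common shift), against 84–100% for the direct tests.

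**4. Why the structure decides it.** A block of k standardised variables with common correlation r has a leading eigenvalue of 1 + (k − 1)r. Take r = 0.3 among the questionnaires as an illustration. One factor over 40 variables gives 1 + 39 × 0.3 = 12.7; two factors of 20 give 1 + 19 × 0.3 = 6.7 each. A common centre effect at 40% of CPA variance, with no other correlation among the CPAs, gives 1 + 5 × 0.4 = 3.0 for 6 tests and 1 + 11 × 0.4 = 5.4 for 12. With one questionnaire factor the sensory block can take PC2. With two, both plotted components are filled first.

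**5. Effect on the APS–CPA correlation.** If centre accounts for a share s of CPA variance and is unrelated to APS, the pooled correlation is the within-centre correlation times √(1 − s) (exact for linear correlation, approximate for ranks). At s = 0.1, 0.2 and 0.4 the factor is 0.95, 0.89 and 0.77. If centres also differ in APS, the distortion can go either way.

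**The case against.** The colour conflict is a one-line correction, and colouring a PCA by centre is a reasonable descriptive screen in an exploratory plan. Beyond that, a reader might infer three stronger things that the documents do not support.

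- *That this is the only planned use of centre.* It is not: centre is nominally in scope in A2.3, I2 and A3. The table templates named in SAP 6.1 were also not available, so by-centre columns cannot be excluded. What stands is that this is the only explicit check in the text.
- *That the plot would miss site effects.* The documents give no correlation structure, number of centres or effect size. With one questionnaire factor and a common shift, the plot does as well as direct testing. Protocol 8.2.1 can also yield more than 10 CPA values per patient, which makes the sensory block easier to see. What stands is that it could miss them.
- *That site shifts contaminate the clustering and the prediction models.* Secondary objective 1 defines the groups by personality traits and disease history, without CPAs. SAP 4.2 keeps CPAs apart from the patient characteristics, and the pain measures named in A1.4 do not include them. Their entry into those analyses is ambiguous.

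There is also mitigation. SA, DMA and TPS sensations are judged against the patient's own control area, which may offset part of an examiner or device shift; the SA and DMA devices are specified as standardised and calibrated; and Protocol 13 provides site training. The simulated effects allow for none of this. None of it, however, removes the contradiction or supplies a comparison of CPAs between sites.

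**Conclusion.** The point holds in this form. The text and legend of Figure 1 contradict each other, and following the legend removes the SAP's only explicit centre check. Restoring the centre colours would give a check of unpredictable sensitivity for the sensory tests: about 5% to 100% at n = 140, against about 77% to 100% for direct tests. The low end arises when questionnaire variation fills both plotted components. That is plausible, since the questionnaires span personality, pain and quality of life, but it is not established. These figures rest on assumed centre numbers, variable counts, effect sizes and correlations; only n comes from the documents.

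The clearest exposure is secondary objective 2 and the APS–CPA correlation endpoint. Harm to the primary objective is not shown. The change is worth making because it is cheap and serves a purpose the SAP itself states.

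**What to change.** 1. Reconcile SAP 5.1.3 with the Figure 1 legend, for example colour for centre and symbol for cluster, or two panels.
2. Add to A1 a by-centre summary of the baseline variables, at minimum each CPA variable, with Kruskal-Wallis tests (Fisher for nominal variables), BH-corrected. At the interim, a non-significant result should not be read as absence of a centre effect.
3. Pre-specify, whatever those tests show, a sensitivity version of the APS–CPA correlation, stratified by centre or centred within centre, with small centres pooled by a rule fixed in advance. Do the same for the clustering if CPAs are used in it. Report it beside the unadjusted result. Centring only those variables that test significant would be a data-driven pre-test and should be avoided.

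The cost is a legend edit, one table and one sensitivity analysis, all from data already collected. Within-centre centring also removes true case-mix differences between sites, so the unadjusted result should stay primary.
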